Clinical Development

QGE031/Ligelizumab

CQGE031G12301 / NCT04984876

A 52 week, multi-center, randomized, double-blind placebo-controlled study to assess the clinical efficacy and safety of ligelizumab (QGE031) in decreasing the sensitivity to peanuts in patients with peanut allergy

Statistical Analysis Plan (SAP)

Document type: SAP Documentation Amendment 3

Release date: 11-September-2023

Number of pages: 48

Property of Novartis

Confidential

May not be used, divulged, published or otherwise disclosed
without the consent of Novartis

Template Version 4.0, Effective from 23-Apr-2021

Document History – Changes compared to previous final version of SAP

Date	Time point	Reason for update	Outcome for update	Section and title impacted (Current)
13 July 2021	Prior to DB lock	Creation of final version	N/A - First version	NA
28 July 2023	After Protocol Amendment 1 and before Dry run	Recruitment halt with the intention to terminate study early. Aligned with protocol amendment 1. Analyses changed.	Removed references to the second CSR	Section 1
			Described changes from early study termination and recruitment halt.	Section 1.1
			Removed analysis concerning sustainability of effect at Week 52.	Section 2.6.4
			Analysis of children under 12 years old removed, due to recruitment halt. Specific output to be presented at Primary Analysis listed. Analysis at Week 52 removed. DMC information added.	Section 2.13
			Due to halt of recruitment, sentences about children 6-11 years old removed.	Section 3
			[REDACTED]	[REDACTED]
			Handling of intercurrent events was simplified, with COVID-19 no longer being an intercurrent event and composite variable strategy being used consistently across endpoints. (Section 2.7.3 on 'Handling of Intercurrent Events' was deleted).	Section 1.2.1 and Section 1.2.2
			[REDACTED] the independent DMC is described.	[REDACTED]
			Treatment group labels are described.	Section 2.1.1.1
			The maximum tolerated dose is defined.	Section 2.1.1.5
			Described how mis-randomized patients are analyzed. PRO data collected removed and described elsewhere.	Section 2.2
			Potential subgroup analysis to split data according to notification of recruitment halt was added. Removed separate analysis for Japanese patients	Section 2.2.1
			Changes to how the number of patients will be summarized for patient disposition and included 12-week timepoint.	Section 2.3.1
			Added additional categories of baseline characteristics for summary.	Section 2.3.2

Added information about prior medications, concomitant medications, and epinephrine use. Replaced summaries by ATC classification by primary system organ class and MedDRA preferred term.	Section 2.4.2
Added log-transformed MTD (Maximum Tolerated Dose) at screening DBPCFC as covariate in logistic regression model. Added P-value will be generated with a likelihood ratio test.	Section 2.5.2
Removed tipping point analyses as missing data due to intercurrent events will be handled with relative conservative strategy (i.e., composite variable strategy)	Section 2.5.3
Added Kaplan-Meier plot and modified marginal standardization analysis.	Section 2.5.4
Maximum tolerated dose analyses and skin prick test described in more detail.	Section 2.6.4
Pooling periods for safety analyses described elsewhere (Section 2.1.1.1).	Section 2.7
Added details on treatment-emergent adverse events.	Section 2.7.1
Added exposure-adjusted incidence rate.	Section 2.7.1.1
Added details for summarizing injection site reactions.	Section 2.7.1.2
Imputation methods described for values that are abnormal or outside the level of quantification.	Section 2.7.3 and Section 2.8
Details on ECG parameters provided.	Section 2.7.4.1
[REDACTED]	[REDACTED]
IgE levels specified as at screening.	Section 2.9
Age groups and scoring of PRO instruments clarified, including SF-6Dv2.	Section 2.10.1
Analysis for PRO scores described.	Section 2.10.1.1
[REDACTED]	[REDACTED]
Power calculations updated using PASS Version 11. Paragraph on consistency trend across age groups removed.	Section 3.1
Sentence about potentially increasing sample size for covid impact was removed. Power table for children 6-11 removed.	Section 3.2
Table on precision levels for safety incidence rate per age group removed.	Section 3.2.1
Changes to protocol specified analyses noted.	Section 4
Details for multiple imputation added, for maximum tolerated dose, binary endpoints involving logistic regression, and marginal standardization. Tipping point analysis for primary estimand removed.	Section 5.4.1
For maximum severity of symptoms, covariates were specified and details on imputation strategy added.	Section 5.4.2
IgE specified as being measured at screening.	Section 5.4.2.1

11 Sep 2023	Before database lock	Clarification of analyses	Specified calculation of negative control for skin prick test mean diameters.	Section 2.6.4
			Removed SF-36 output from Table 2-2 and specified missing data approach for additional analysis	Section 2.13

Table 3-3 Precision levels (95% CI) for sensitivity of safety incidence rate for overall population 40
Table 5-1 Notable values requiring further evaluation for Heart Rate (HR) and Blood Pressure in children and adolescents 44

Table 5-2 Criteria leading to exclusion47

List of figures

Figure 1-1 Study design 11
Figure 2-1 Testing strategy24

List of abbreviations

█	█
AE	Adverse Event
ANCOVA	Analysis of covariance
ATC	Anatomical Therapeutic Chemical
AUC	Area under Curve
bpm	Beats per minute
CD23	IgE (low affinity) receptor
CI	confidence intervals
CM	Concomitant Medication
Covid-19	Corona Virus Disease 2019
CRF	Case Report/Record Form (paper or electronic)
CSR	Clinical study report
CV	Coefficient of variation
DBL	Database Lock
DBPCFC	Double Blind Placebo Controlled Food Challenge
DMC	Data Monitoring Committee
█	█
ECG	Electrocardiogram
eCRF	Electronic case report form
EOS	End of study
FAIM	Food Allergy Independent Measure
FAQLQ	Food Allergy Quality of Life Questionnaire
FAS	Full Analysis Set
FcεRI	IgE (high affinity) receptor
gMCP	Graph Based Multiple Comparison Procedures
h	Hour
HRQoL	Health-Related Quality of Life
IgE	Immunoglobulin E (specific and un-specific for the study allergen)
IgG	Immunoglobulin G
L	Liter
LLOQ	Lower limit of quantification
MAR	Missing at random
MedDRA	Medical dictionary for regulatory activities
mg	Milligram(s)
mL	Milliliter(s)
mm	Millimeter
mmHg	Blood pressure unit millimeters of mercury
MRI	Magnetic Resonance Imaging
ms	Millisecond
MTD	Maximum Tolerated Dose
OFC	Oral Food Challenge
█	█
█	█
PRO	Patient Reported Outcomes
q4W	Every 4 weeks

RAS	Randomized Analysis Set
RR	Responder rate
SABA	Short-acting β -agonist
SAE	Serious Adverse Event
SAF	Safety analysis set
SC	Subcutaneous
SCq4W	Subcutaneous injection every 4 weeks
SD	Standard deviation
slgE	Specific IgE for the study allergen
SMQ	Standardized MedDRA Query
SPT	Skin Prick Test
Total IgE	Drug-bound and free IgE
μ L	Microliter
ULOQ	Upper limit of quantification

1 Introduction

The purpose of this document is to describe the statistical analyses mentioned in version 01 (amendment 1) of the Phase 3 study CQGE031G12301 protocol.

This document covers statistical and analytical plans for the primary endpoint analysis (i.e., after all participants have completed the visit at Week 12) and the final analysis (i.e., after all participants have completed the follow-up visit or prematurely withdrawn from the study).

[figure not shown]
1.1 Study design

This is a 52-week, Phase 3 multi-center, randomized, double-blind and placebo-controlled study to assess the safety and clinical efficacy of ligelizumab (QGE031) in participants with a medically confirmed diagnosis of IgE-mediated peanut allergy. The primary objective of the study is to evaluate the efficacy of ligelizumab 240 mg and 120 mg (SCq4w) compared to placebo at Week 12, as measured by the proportion of participants who can tolerate a single dose of ≥ 600 mg (1044 mg cumulative tolerated dose) of peanut protein without dose-limiting symptoms during the double-blind, placebo controlled, food challenge (DBPCFC).

A total sample size of approximately 486 randomized participants aged 6 to 55 years was initially planned. Due to the decision of halt recruitment and terminate the study early ([Section 4](#)), the final size is 211, with only adolescent and adult participants being recruited. Participants were randomized at a 2:2:2:2:1 ratio to one of five treatment arms at the time of randomization visit as follows:

- Ligelizumab 240 mg SC q4w
- Ligelizumab 120 mg SC q4w
- Placebo 8 weeks to Ligelizumab 240 mg SC q4w
- Placebo 8 weeks to Ligelizumab 120 mg SC q4w
- Placebo 16 weeks to Ligelizumab 240 or 120 mg SC q4w (with a ratio of 0.5 : 0.5 for switched treatment)

Participants will be stratified based on region, total IgE at screening (<350 IU/ mL; ≥ 350 IU/ mL) and age (12 - 17y, and 18 - 55y).

Figure 1-1 Study design

• N = 486

The study will include the following:

1. **Screening period (Duration of 4 weeks)**

2. **Treatment period (Duration of 52 weeks)**

- **Double-blind placebo-controlled treatment period (Duration of 12 weeks):** Study participants will be seen in the clinic at Day 1, Week 1, Week 4, Week 8 and Week 12. The DBPCFC will be performed at Week 12. Participants assigned to the 8-week placebo arms will receive the first dose of blinded ligelizumab treatment at the Week 8 visit. Participants assigned to the 16-week placebo arm will receive the first dose of blinded ligelizumab treatment at the Week 16 visit.
- **Long-term active blinded (no placebo control) treatment period (Duration of 40 weeks/ 36 weeks for participants on the 16-week placebo arm):** Starting at Week 16, all study participants will receive blinded ligelizumab study treatment in the clinic every 4 weeks until Week 52. A final DBPCFC will be performed at Week 52.

3. **Post-treatment follow-up period (Duration of 16 weeks):** There are 4 planned clinic visits (every 4 weeks). Study evaluations include safety, [REDACTED], post-treatment biomarkers. Study treatment is not given and there is no DBPCFC.

At the start of the study, recruitment was restricted to 12 - 55 year old participants. When approximately 60 adolescent participants (defined as 12 -17 years of age) would have completed all Week 12 assessments, an interim analysis [REDACTED] was to be performed for confirmation of the pediatric dose (safety will be reviewed by a Data Monitoring Committee - DMC). Independent sponsor members who are responsible for [REDACTED] Modeling & Simulation will be unblinded to the results of this interim analysis.

As Novartis decided to halt recruitment (Date of issuing halt notification: 05 Apr 2023) with the intention to terminate the study early, there will be no recruitment of children under age 12.

Patients who are already in the study (i.e., signed informed consent) at the time of the halt notification will be managed according to their individual progress within the study as described in the table below.

[figure not shown]
Group 1	Already completed Week 52 Visit assessments	Complete the 16-week safety follow up period as per protocol
Group 2	Already completed Week 12 Part 2 Visit	Attend the next scheduled visit (as per schedule of events), which will now correspond to the end of treatment visit (Week 52 Part 1). Patients will be informed at that visit that the treatment is stopped (no drug administration at that visit) and that they will enter the 16-week follow up period as per protocol. Notably, no oral food challenge will be done at this end of treatment visit
Group 3	Randomized but have not yet reached the Week 12 Part 2 Visit	At their next visit, investigators should inform the patient of the study status and provide them with the opportunity to continue and perform the assessments until week 12 Part 2. The week 12 Part 2 visit will now be considered end of treatment (Week 52 Part 2) so that afterwards patients will then enter the 16-week safety follow up period as per protocol. In this situation, there is no need to fill out the "Trial Feedback Questionnaire."
Group 4	Reached the Screening Visit 2 Part 1	Allowed to complete the Screening Visit 2 Part 2 (i.e., complete both parts of the baseline Oral Food Challenge) and, pending final eligibility, to be randomized and continue as patients in Group 3.
Group 5	In screening period but have not reached the Screening Visit 2 Part 1	Screening failed and patients will be eligible for future pivotal studies

1.2 Study objectives, endpoints and estimands

Table 1-1 Objectives and related endpoints

Objective(s)	Endpoint(s)
Primary objective(s)	Endpoint(s) for primary objective(s)

 To evaluate the efficacy of ligelizumab 240 mg and 120 mg (SCq4w), compared to placebo, as measured by the proportion of participants who can tolerate a single dose of ≥ 600 mg (1044 mg cumulative tolerated dose) of peanut protein without dose-limiting symptoms during the DBPCFC at Week 12 	
 Responder status defined as tolerating a single dose of ≥ 600 mg (1044 mg cumulative tolerated dose) of peanut protein without dose-limiting symptoms during the DBPCFC conducted at Week 12.
Secondary objective(s)	Endpoint(s) for secondary objective(s)

 Key secondary objectives To evaluate the efficacy of ligelizumab 240mg and 120mg (SCq4w), compared to placebo, as measured by the proportion of participants who can tolerate a single dose of ≥ 1000 mg (2044 mg cumulative tolerated dose) of peanut protein without dose-limiting symptoms during the DBPCFC at Week 12 	
 Key secondary endpoints Responder status defined as tolerating a single dose of ≥ 1000 mg (2044 mg cumulative tolerated dose) of peanut protein without dose-limiting symptoms during the DBPCFC conducted at Week 12.

 To evaluate the efficacy of ligelizumab 240mg and 120mg (SCq4w), compared to placebo, as 	
 Responder status defined as tolerating a single dose of 3000 mg (5044 mg cumulative tolerated

Objective(s)	Endpoint(s)

measured by the proportion of participants who can tolerate a single dose of 3000 mg (5044 mg cumulative tolerated dose) of peanut protein without dose-limiting symptoms during the DBPCFC at Week 12
 
 • To evaluate the efficacy of ligelizumab 240mg and 120mg (SCq4w), compared to placebo, as measured by the maximum symptom severity at any single challenge dose up to and including 1000 mg of peanut protein during the DBPCFC at Week 12 • To evaluate the efficacy of 8 weeks of placebo treatment followed by 4 weeks of ligelizumab 120 mg / 240 mg (SCq4w) treatment compared to 12 weeks of placebo treatment, as measured by the proportion of participants who can tolerate a single dose ≥ 1000 mg of peanut protein without dose-limiting symptoms during the DBPCFC at Week 12 • Other secondary objectives • To evaluate the efficacy of ligelizumab 240mg and 120mg (SCq4w), as measured by the proportion of participants who can tolerate a single dose of ≥ 1000 mg (2044 mg cumulative tolerated dose) of peanut protein without dose-limiting symptoms during the DBPCFC at Week 52 compared to Week 12 • To evaluate the effects of ligelizumab 240 mg and 120 mg (SCq4w), compared to placebo (when applicable), as measured by multiple systemic biomarkers to inform on response to treatment or disease severity • To evaluate the safety and tolerability of ligelizumab 240 mg and 120 mg (SCq4w) • To assess the ability of IgE suppression to impact skin mast cells through the assessment of allergen-specific skin prick test (SPT). • To evaluate the impact of ligelizumab on the health-related quality of life (HRQoL) of patients with peanut allergy. 	
dose) of peanut protein without dose-limiting symptoms during the DBPCFC conducted at Week 12.
 
 • Maximum severity of symptoms occurring at any challenge dose of peanut protein up to and including 1000 mg during the DBPCFC conducted at Week 12. Symptom severity will be categorized as 4 levels: None, Mild, Moderate, Severe. • Responder status defined as participants tolerating a single dose of ≥ 1000 mg (2044 mg cumulative tolerated dose) of peanut protein without dose-limiting symptoms during the DBPCFC conducted at Week 12 (8 weeks of placebo + 4 weeks of ligelizumab treatment vs. 12 weeks of placebo). • Other secondary endpoints • Proportion of participants tolerating a single dose of ≥ 1000 mg (2044 mg cumulative tolerated dose) of peanut protein without dose-limiting symptoms during DBPCFC conducted at Week 52 • Change in maximum tolerated dose (MTD) of peanut protein without dose-limiting symptoms during the DBPCFC at Week 52 compared to Week 12 • Change from baseline at Week 12, 16 and Week 52 of 
 •peanut-specific IgE •peanut-specific IgG4 • Summaries of treatment-emergent adverse events, vital signs, ECG, and laboratory values • Change from baseline (screening) in SPT mean wheal diameters at Week 16, Week 56 and Week 68. • Change from baseline in total and domain scores in the FAQLQ, FAIM, and SF-36v2 by age and responder (subject and/or caregiver) at various points in time.

Objective(s)	Endpoint(s)

1.2.1 Primary estimand(s)

The primary estimand quantifies the effects of ligelizumab 120mg and 240mg SCq4w as compared to placebo on the proportion of responders at Week 12 regardless of intake of rescue medication prior to Week 12.

The primary estimand is described by the following attributes:

- **Population:** participants who have been diagnosed with IgE-mediated peanut allergy and met study inclusion/exclusion criteria.
- **Variable:** Responder status defined as tolerating a single dose of ≥ 600 mg (1044 mg cumulative tolerated dose*) of peanut protein without dose-limiting symptoms **during the DBPCFC conducted at Week 12.
- **Treatment:** the randomized treatment[^] (ligelizumab 120mg SCq4w, ligelizumab 240mg SCq4w, and placebo) plus rescue medication (e.g., epinephrine, SABA, anti-histamines), if needed.
- **Handling of intercurrent events:**
 - Discontinuation of treatment or missing more than one dose prior to Week 12: participants who discontinue treatment or miss more than one dose prior to Week 12 will not undergo any DBPCFC. They will be considered non-responders (*composite variable strategy*).
 - Intake of rescue medication prior to DBPCFC conducted at Week 12: ignorable (*treatment policy strategy*, reflected in the Treatment attribute)
Epinephrine, SABA, anti-histamines and saline bolus are typically used as rescue medication to treat allergic reactions. Participants who experience allergic reactions due to accidental exposure or other reasons may need to take rescue medications prior to Week 12. However, participants must be in good health before proceeding with the food challenge and meet the washout requirement of permitted medications as described in Protocol Table 6-2. Therefore, to reflect clinical practice, all observed values after this intercurrent event will be used in the statistical analyses whenever the treatment effect is estimated.

- **Summary measure:** odds ratio comparing the proportion of responders between each ligelizumab dose group and placebo group
- **The cumulative tolerated dose is the sum of the tolerated doses, not including the reactive dose (Casale et al 2019)*
- ***Dose-limiting symptoms indicate a true allergic reaction occurring during administration of a single dose of peanut protein at the DBPCFC that should preclude the administration of any further doses in the view of the investigator. Symptoms that require administration of any rescue medication are considered dose-limiting symptoms.*
- *^ The randomized treatment indicates ligelizumab 120 mg arm, ligelizumab 240 mg arm, and placebo 16wk to ligelizumab 120/240 mg arm (labelled as placebo for efficacy estimands).*

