### 12.4.2 Statistical model, hypothesis, and method of analysis

The trial will be considered positive, if at least one of the two ligelizumab doses demonstrate a statistically significant result in comparing the proportion of responders as described below. The two doses will be tested in parallel for 12 weeks treatment on the primary endpoint.

Let  $p_j$  denote the responder rate for treatment regimens  $j$ ,  $j=0, 1$  or  $2$  where

- 0 corresponds to placebo
- 1 corresponds to ligelizumab 120 mg treated for 12 weeks
- 2 corresponds to ligelizumab 240 mg treated for 12 weeks

Responder rate is defined as the proportion of participants tolerating a single dose of  $\geq 600$  mg (1044 mg cumulative tolerated dose) of peanut protein without dose-limiting symptoms during the DBPCFC conducted at Week 12. For participants with treatment discontinuation or missing more than 1 doses of study drug prior to Week 12 due to reasons other than operational complications caused by public health emergency, they will be considered non-responders.

The following hypotheses will be tested:

$H_{0\ 120\ RR600} : p_1 / (1 - p_1) \leq p_0 / (1 - p_0)$  versus  $H_{A\ 120\ RR600} : p_1 / (1 - p_1) > p_0 / (1 - p_0)$

$H_{0\ 240\ RR600} : p_2 / (1 - p_2) \leq p_0 / (1 - p_0)$ ,  $H_{A\ 240\ RR600} : p_2 / (1 - p_2) > p_0 / (1 - p_0)$

$H_{0\ 120\ RR600}$ : ligelizumab 120mg is not superior to placebo with respect to the responder rate at a level of 600 mg peanut protein (1044 mg cumulative tolerated dose) without dose-limiting symptoms at Week 12

$H_{0\ 240\ RR600}$ : ligelizumab 240mg is not superior to placebo with respect to the responder rate at a level of 600 mg peanut protein (cumulative tolerated dose 1044 mg) without dose-limiting symptoms at Week 12

The primary endpoint will be analyzed based on a logistic regression model, including treatment, age subgroup (6 – 11 years, 12 –17 years, 18 - 55 years), region as fixed class effects and log-transformed total IgE at Screening Visit 1 as a covariate. Odds ratio and 95% confidence intervals (CI) will be presented comparing each Ligelizumab dose to Placebo with respect to the proportions of responders.

The detailed testing strategy for primary and key secondary endpoints is provided in [Section 12.5.1](#).

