2.5.2 Statistical hypothesis, model, and method of analysis

The trial will be considered positive, if at least one of the two ligelizumab doses demonstrates a statistically significant result in comparing the proportion of responders as described below. The two doses will be tested in parallel for 12 weeks treatment on the primary endpoint.

Let p_j denote the responder rate for treatment regimens j , $j=0, 1$ or 2 where

- 0 corresponds to placebo
- 1 corresponds to ligelizumab 120 mg treated for 12 weeks
- 2 corresponds to ligelizumab 240 mg treated for 12 weeks

Responder rate is defined as the proportion of participants tolerating a single dose of ≥ 600 mg (1044 mg cumulative tolerated dose) of peanut protein without dose-limiting symptoms during the DBPCFC conducted at Week 12. For participants with treatment discontinuation or missing more than 1 doses of study drug prior to Week 12 due to reasons other than operational complications caused by public health emergency, they will be considered non-responders.

The following hypotheses will be tested:

H_0 120 RR600 : $p_1 / (1 - p_1) \leq p_0 / (1 - p_0)$ versus H_A 120 RR600 : $p_1 / (1 - p_1) > p_0 / (1 - p_0)$

H_0 240 RR600 : $p_2 / (1 - p_2) \leq p_0 / (1 - p_0)$, H_A 240 RR600 : $p_2 / (1 - p_2) > p_0 / (1 - p_0)$

H_0 120 RR600 : ligelizumab 120mg is not superior to placebo with respect to the responder rate at a level of 600 mg peanut protein (1044 mg cumulative tolerated dose) without dose-limiting symptoms at Week 12

H_0 240 RR600 : ligelizumab 240mg is not superior to placebo with respect to the responder rate at a level of 600 mg peanut protein (cumulative tolerated dose 1044 mg) without dose-limiting symptoms at Week 12

The primary endpoint will be analyzed based on a logistic regression model, including treatment, age subgroup (12 – 17 years, 18 – 55 years), region as fixed class effects, as well as log-transformed total IgE at screening and log-transformed MTD (Maximum Tolerated Dose) at screening DBPCFC as covariates. P-value will be generated with a likelihood ratio test. Odds

ratio and 95% profile likelihood confidence intervals (CI) will be presented comparing each ligelizumab dose to placebo with respect to the proportions of responders.

The detailed testing strategy for primary and key secondary endpoints is provided in [Section 2.6.2](#).

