2.5.4 Supplementary analyses

Two supplementary analyses will be performed for the primary endpoint.

Marginal Standardization

The first supplementary estimand is the same as for the primary estimand except that the summary measure is the risk difference for marginal proportions of responders. The risk difference will be derived from the predicted risks for every patient as if they had received each treatment using a logistic regression model ([Ge et al 2011](#)). The model will include the same terms as in the primary analysis. The estimated treatment group risks, risk difference and 95% CI will be presented. Details are provided in [Section 5.4.1](#).

Kaplan-Meier plot

A Kaplan-Meier plot will show the probability of experiencing a dose-limiting symptom during dose escalation of DBPCFC at Week 12 by treatment group. The dose of peanut protein at which dose-limiting symptom occurs during the DBPCFC at Week 12 will be treated as the time variable. There will be two separate plots showing those who completed DBPCFC at Week 12: the first will show the results for the overall population; the second will be stratified by the highest tolerated dose of peanut protein at baseline (< 30 mg or >= 30mg). Participants' maximum tolerated dose may be censored if they:

- tolerated 3000mg of peanut protein; or
- completed a certain level of challenge dose without experiencing dose-limiting-symptoms and chose to stop the DBPCFC before beginning or finishing a higher challenge dose (for example, due to the taste of the challenge material).

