3.2.1 Precision for adverse events

Table 3-3 Precision levels (95% CI) for sensitivity of safety incidence rate for overall population

Event rate (proportion of participants with an event)	Number of participants	95% CI
0%	486	(0%, 0.8%)
1%	486	(0.3%, 2.3%)
2%	486	(1%, 3.7%)
0%	211	(0%, 1.7%)
1%	211	(0.1%, 3.5%)
2%	211	(0.6%, 4.9%)

4 Change to protocol specified analyses

On 31 March 2023, Novartis made a strategic decision to close recruitment in study CQGE031G12301 and terminate the study early. As a result, there are several changes to the specified analyses in the protocol, namely:

- Instead of 486 participants, the sample size is 211.

- There will be no recruitment of children under age 12, and the age-groups of interest are now 12-17 and 18-55.
- For participants who have reached Screening Visit 2 Part 1 and not completed Week 52 visit at the time of halt recruitment will need to complete Screening Visit 2 Part 2 to determine eligibility. If they are eligible, they will either continue treatment and perform assessments until Week 12 Part 2 or will stop treatment at the next scheduled visit if they have already completed Week 12 Part 2. This leads to limited number of participants reaching Week 52. Hence, non-inferiority test for sustainability of treatment effect at Week 52 compared to Week 12 is removed.
- Week 52 interim analysis will not be conducted.

There are also some changes made to simplify the analyses:

- Since the number of COVID-19 related intercurrent events is expected to be minimal, references to COVID-19 related intercurrent events were removed.
- Handling of intercurrent events for the secondary estimands were changed to be consistent with the primary estimand strategy.
- The two-dimensional tipping point analysis for the primary estimand was removed.

In analysis for primary estimand and secondary estimands(1, 2 and 4), log-transformed MTD at screening DBPCFC was added as covariate in logistic regression models.

The protocol mentions the summary measure of supplementary estimand is relative risk generated with a marginal standardization method. In SAP, relative risk is changed to risk difference to facilitate clinical interpretation.

5 Appendix

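### The primary summary measure is the odds ratio of two responder proportions, but the reported figure is a covariate-conditional odds ratio, which is further from 1 if the covariates are prognostic

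*SAP*

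**What the plan says.** **Target.** SAP 1.2.1 states the summary measure as the "odds ratio comparing the proportion of responders between each ligelizumab dose group and placebo group". SAP 2.5.2 defines p_j as "the responder rate for treatment regimens j" and sets the null hypotheses as p_j/(1−p_j) no greater than p_0/(1−p_0). No covariate appears in either place.

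**Estimate.** SAP 2.5.2 then fits a logistic model with treatment, age group and region, "as well as log-transformed total IgE at screening and log-transformed MTD (Maximum Tolerated Dose) at screening DBPCFC as covariates". It reports an odds "ratio and 95% profile likelihood confidence intervals (CI) will be presented comparing each ligelizumab dose to placebo".

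**Change from the protocol.** Protocol 12.4.2 had the same structure, with "log-transformed total IgE at Screening Visit 1 as a covariate" and no MTD term. SAP Section 4 records that, for the primary estimand and secondary estimands 1, 2 and 4, "log-transformed MTD at screening DBPCFC was added as covariate in logistic regression models". The summary measure was left as it was.

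**Marginal analysis.** SAP 2.5.4 plans standardisation as a supplementary analysis of the primary endpoint. It differs from the primary estimand in that "the summary measure is the risk difference for marginal proportions of responders". The method is given: "The risk difference will be derived from the predicted risks for every patient as if they had received each treatment using a logistic regression model". A marginal odds ratio is not planned.

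**The concern.** The estimand and the hypotheses are functions of two group proportions. The treatment coefficient of an adjusted logistic model is the odds ratio between participants who share the same age group, region, total IgE and screening MTD. The two agree when treatment has no effect or the covariates are not prognostic. Otherwise the conditional odds ratio is further from 1, even under perfect randomisation, because the odds ratio is non-collapsible.

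No visible text says which of the two is meant. A profile likelihood interval belongs to a model coefficient, and SAP 2.5.4 brings in marginal proportions as a departure from the primary estimand. The reported figure is therefore the conditional one.

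What is at stake is the estimate and its label. A reader who forms the odds ratio from the responder rates will not recover the headline figure. The quantity that figure targets also depends on which covariates are in the model.

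**Working it through.** **Inputs.** From SAP 3.1: responder rates of 68% (ligelizumab) and 17% (placebo) in randomised participants, built from 80% and 20% among those evaluable with 15% dropout counted as non-response; about 46 v 23 participants per comparison; one-sided level 0.0125. Assumed, because the documents give no prognostic strength: a normally distributed covariate score with standard deviation (SD) 0.5, 1.0 or 1.5 on the logit scale.

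**Step 1: the plan's own figure.** Exact power of the one-sided Fisher test, by enumerating both binomials, is 96.5% at 68% v 17% (stated 96%) and 85.8% at 59.5% v 17% (stated 86%). The stated power reproduces. It rests on unadjusted proportions, so it does not depend on this point.

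**Step 2: the odds ratio that SAP 1.2.1 names.** (0.68/0.32) / (0.17/0.83) = 2.125/0.2048 = 10.4.

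**Step 3: covariates act directly on the composite outcome.** For each SD s, solve for the intercepts a1 and a0 at which the average of 1/(1+exp(−a−sZ)) over standard normal Z equals 0.68 and 0.17. The conditional odds ratio is exp(a1−a0). For s = 1.0, a1 = 0.907 and a0 = −1.879, giving exp(2.786) = 16.2.

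**Step 4: covariates act on evaluable response.** Solve for the intercepts at 0.80 and 0.20, multiply the response probabilities by 0.85 (dropout at random), and find the large-sample limit of the adjusted logistic fit with 2:1 allocation. The marginal rates are again 68% and 17%.

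| Covariate SD (logit) | Odds ratio of proportions | Adjusted, acting on evaluable response | Adjusted, acting on composite |
|---|---|---|---|
| 0.5 | 10.4 | 11.0 (+6%) | 11.7 (+13%) |
| 1.0 | 10.4 | 12.8 (+23%) | 16.2 (+56%) |
| 1.5 | 10.4 | 15.3 (+48%) | 25.4 (+145%) |

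Averaging the predicted risks from the Step 4 fits returns 68% and 17%, and so an odds ratio of 10.4 in every row.

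**Step 5: what adding MTD could do.** Assume the five screening MTD levels are equally likely, total IgE has a log odds slope of 0.25 or 0.5 per SD, and MTD has the odds ratio shown per 10-fold increase. Large-sample adjusted odds ratios, first with IgE only and then with IgE and MTD:

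| IgE slope | MTD odds ratio per 10-fold | Acting on evaluable response | Acting on composite |
|---|---|---|---|
| 0.25 | 1.5 | 10.5 to 10.7 | 10.7 to 11.2 |
| 0.5 | 2 | 10.9 to 11.6 | 11.7 to 13.2 |
| 0.5 | 3 | 11.0 to 12.6 | 11.6 to 15.6 |
| 0.5 | 5 | 10.9 to 14.0 | 11.2 to 21.0 |

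The standardised odds ratio from the same models stayed between 10.3 and 10.5. With no prognostic value for MTD beyond the other terms, adding it would not move the target.

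**Step 6: secondary endpoints.** With the planned rates of SAP Table 3-2 and the Step 3 method, 1000 mg (59.5% v 17%) gives 7.2 for the proportions and 7.9 to 15.2 conditional. For 3000 mg (51% v 12.75%) it gives 7.1 and 7.8 to 14.4. These are composite-outcome figures, so they sit at the higher end.

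**The case against.** **Size.** The composite-outcome range is not the natural reading of the SAP's own response structure, which separates evaluable response from dropout. On that structure the range is 11.0 to 15.3. An SD of 1.5 is also demanding: screening MTD takes only five values (below 1, 1, 3, 10 and 30 mg), and with equal weights and zero set to 0.3 mg its log10 SD is 0.71. To give SD 1.5 alone, MTD would need an odds ratio of exp(1.5/0.71), about 8, per 10-fold increase; SD 1.0 would need about 4. This stands, and both ranges are shown for that reason.

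**Precision.** At 46 v 23, an unadjusted Wald 95% interval around 10.4 runs from about 3.0 to 36, which covers every adjusted value above. That is true, but sampling error does not excuse reporting a different quantity from the one named, and the shift goes in one direction.

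**Marginal results are already planned.** SAP 2.5.4 and Table 2-2 include standardised risks at 600 mg, so a reader could compute the marginal odds ratio by hand. This is real mitigation for the primary endpoint. It gives no interval on the odds ratio scale and nothing for secondary estimands 1, 2 and 4.

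**Unseen detail.** SAP 5.4.1 is not visible and may say more. It would not remove the mismatch between 1.2.1 and the interval specified in 2.5.2.

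**Stronger readings that the documents do not support.** A reader might infer that the type I error is compromised. It is not, because both odds ratios equal 1 when treatment has no effect. A reader might infer that covariate adjustment is wrong, but it is sound. A reader might infer that adding MTD did widen the gap. The SAP uses screening MTD as covariate, subgroup factor and Kaplan-Meier stratifier but never quantifies its prognostic strength, so *could widen* is as far as one can go.

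**Conclusion.** The mismatch is real and concerns estimation and labelling. SAP 1.2.1 and the hypotheses name an odds ratio of two proportions, and SAP 2.5.2 reports a conditional one. The direction follows from non-collapsibility whenever treatment works and the covariates are prognostic. The size rests on assumptions about covariate strength and about how dropout enters: 10.4 against roughly 11.0 to 15.3 on the SAP's evaluable-then-dropout structure, or up to 25.4 if the covariates act on the composite. With weak covariates it is minor (10.7 at SD 0.25 on the composite). The effect of adding MTD is conditional on its being prognostic beyond the other terms. The likelihood ratio test, the alpha split, the graphical procedure and the stated power stand. The point should be settled in the SAP because it bears on the headline effect estimate of a Phase 3 trial, but it does not threaten the trial's conclusion.

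**What to change.** Keep the adjusted logistic model and the likelihood ratio test. Then:

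- Label the model coefficient *odds ratio conditional on age group, region, total IgE and screening MTD*.
- Report beside it the marginal odds ratio, p1(1−p0)/[p0(1−p1)], from the standardised risks of SAP 2.5.4, as the quantity that matches the 1.2.1 summary measure. Give it a confidence interval by the delta method or bootstrap, combined across imputations.
- Do the same for secondary estimands 1, 2 and 4.

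**Cost.** SAP wording plus modest programming. Standardisation is now planned for the primary endpoint only, so the secondary estimands need new output, and the marginal interval needs a specified variance method that works with multiple imputation. A smaller odds ratio will appear alongside the model coefficient, and the p-value will still come from the adjusted model, so a sentence should explain why the two figures differ.
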